Official Title:

Isokinetic Performance After Cruciate-substituting Ultra-congruent and Posterior Stabilized Total Knee Arthroplasties

NCT Number:

1585/2017

Date:

June 08, 2020

OBJECTIVE

Whether ultra-congruent (UC) or posterior cruciate ligament-stabilized (PS) inserts should be used in posterior cruciate ligament (PCL)-sacrificing total knee arthroplasty (TKA) remains debatable. Therefore, the aim of this prospective randomized controlled study is to compare the isokinetic performance and clinical outcomes of these inserts in PCL sacrificing TKA.

DESIGN AND METHODS

Sixty-six patients diagnosed with primary knee osteoarthritis will be randomly assigned to either the UC or the PS group. The Knee Society score (KSS) and isokinetic performance results for each patient will be recorded preoperatively and at 3, 6 and 12 months postoperatively. The physiatrist performing the isokinetic tests and the patients will be blinded to the study groups.

This study is approved by the institutional review board (IRB) by the “Ankara Numune Training and Research Hospital Clinical Research Ethics Committee” ethical committee (1585/2017) (Ankara, Turkey) and will be performed in accordance to the 1964 Helsinki Declaration and its amendments.

STATISTICAL ANALYSIS PLAN (SAP)

Sample size estimation is performed using the mean knee extensor peak torque at one year postoperatively, 53.9 Nm, and the standard deviation, 12, reported in a prior study [1] and G*Power (version 3.1.9.6.) software. A total of 66 patients is estimated to be needed to achieve a power of 95% in detecting a 10 Nm difference in the extensor peak torque, with a standard deviation of 12, 4 measurements, an effect size of 0.41 and a significance level (alpha) of 0.05 using two-way repeated measures ANOVA. All the data will be presented as means and standard deviations. Two-way repeated measures ANOVA will be used for the statistical analysis of the repeated measurements in the two groups. The statistical calculations will be performed with SPSS 22.0 software (IBM SPSS Statistics for Windows, version 22.0. Armonk, NY: IBM Corp.). Values of $p < 0.05$ will be considered statistically significant.

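### The effect size of 0.41 does not describe a 10 Nm post-operative difference in the named four-visit ANOVA, so the 95% power claimed at 66 patients is unsupported

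*Combined protocol and SAP*

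**What the plan says.** The sample-size paragraph of the Statistical Analysis Plan starts from a one-year figure: "Sample size estimation is performed using the mean knee extensor peak torque at one year postoperatively, 53.9 Nm", with an SD of 12 from the same cited study. It then says "A total of 66 patients is estimated to be needed to achieve a power of 95% in detecting a 10 Nm difference" in extensor peak torque, "with a standard deviation of 12, 4 measurements, an effect size of 0.41", at alpha 0.05. The named analysis is the same as the one powered: "Two-way repeated measures ANOVA will be used for the statistical analysis of the repeated measurements in the two groups".

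Design and Methods fixes what the four measurements are. Isokinetic results "will be recorded preoperatively and at 3, 6 and 12 months postoperatively", and patients "will be randomly assigned to either the UC or the PS group".

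The paragraph does not say which ANOVA term the 95% belongs to, what correlation among visits was assumed, or at which visits the 10 Nm is expected. It gives no allocation ratio and no dropout allowance.

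**The concern.** A two-way repeated measures ANOVA has two terms that compare the inserts: the group main effect, which compares averages over all visits, and the group-by-time interaction, which compares profiles. An effect size entered with four measurements has to describe what the treatment does over those four visits. The insert cannot act before surgery, so a post-operative difference is diluted in the group term and appears as a change in profile in the interaction. The value 0.41 allows for neither.

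This is the trial's only power figure. The power of the two terms moves in opposite directions as the correlation rises. Without the term and the correlation, nobody reading a non-significant result can tell whether that test had a good chance of finding 10 Nm.

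**Working it through.** **Inputs from the documents.** N = 66, SD 12, difference 10 Nm, 4 measurements, f = 0.41, alpha 0.05, power 95%; one pre-operative and three post-operative visits; randomised groups. **Assumed here, because not stated:** 33 per group, SD 12 at every visit, equal correlation ρ between all pairs of visits (compound symmetry), no dropout.

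**Step 1: the plan's own figure.** 10/(2 × 12) = 0.4167, written as 0.41.

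- Group term: λ = N × 4 × f²/(1 + 3ρ), F(1, N − 2). With f = 0.41, the N for 95% power is 22 (ρ = 0), 40 (0.3), 52 (0.5), 66 (0.737 to 0.770), 68 (0.8) and 74 (0.9). At ρ = 0.75, λ = 66 × 4 × 0.1681/3.25 = 13.65 and power is 95.35%. With f = 0.4167, 66 arises at ρ of 0.772 to 0.807.
- Group-by-time term, F(3, 3(N − 2)), sphericity assumed. With f = 0.41, λ = N × 4 × f²/(1 − ρ) gives N = 28 at ρ = 0 and fewer at higher ρ; λ = 3(N − 2)f² gives 38; λ = N f² gives 104; λ = (N − 2)f² gives 106.

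The stated inputs therefore fit totals from under 30 to over 100. The figure of 66 cannot be reproduced without supplying inputs that the SAP does not give.

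**Step 2: the effect size that matches the schedule.** Randomisation makes the expected pre-operative difference zero.

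- 10 Nm at 3, 6 and 12 months (0/10/10/10). The four-visit average is 30/4 = 7.5 Nm, so the group-term f = 7.5/24 = 0.3125. The deviations from that average are −7.5, 2.5, 2.5 and 2.5, with sum of squares 56.25 + 3 × 6.25 = 75, so the group-by-time f = √(75/4)/24 = 0.180 on the N × 4 × f²/(1 − ρ) scaling.
- 10 Nm at 12 months only (0/0/0/10). The average is 2.5 Nm, so the group-term f = 2.5/24 = 0.104. The sum of squared deviations is again 75, so the group-by-time f is again 0.180.

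For the group term to have f = 0.41, the difference at each of the three later visits would have to be 0.41 × 24/0.75 = 13.1 Nm.

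**Step 3: power at N = 66.** For the group term under 0/10/10/10, λ = 66 × 4 × 0.3125²/(1 + 3ρ) = 25.78/(1 + 3ρ). For group-by-time under either pattern, λ = 66 × 4 × (75/4)/24²/(1 − ρ) = 8.59/(1 − ρ). For the group term under 12 months only, λ = 66 × 4 × (2.5/24)²/(1 + 3ρ) = 2.86/(1 + 3ρ).

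| ρ | Group, 0/10/10/10 | Group-by-time, either pattern | Group, 12 months only |
|---|---|---|---|
| 0.3 | 95.2% | 84.1% | 23% |
| 0.5 | 88.5% | 94.6% | 18% |
| 0.75 | 79.2% | 99.9% | 15% |

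Simulation of the 0/10/10/10 pattern (20,000 trials each) agrees: 95.4% and 83.9% at ρ = 0.3, 88.5% and 94.8% at 0.5, 79.2% and 99.9% at 0.75 (group, group-by-time). Under 0/10/10/10 the group term reaches 95% for ρ up to 0.308, and group-by-time for ρ of 0.510 or more.

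**Step 4: a 12-month comparison.** Two groups, λ = N d²/4, F(1, 64): 91.5% with d = 10/12 = 0.833, and 90.7% with d = 0.82. Adjusting for pre-operative torque divides λ by (1 − r²), where r is the correlation between pre-operative and 12-month torque, and leaves 63 error degrees of freedom. With d = 0.833, power is 93.8% (r = 0.3), 95.3% (0.4) and 97.1% (0.5). With d = 0.82 it is 93.0%, 94.7% and 96.6%.

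**The case against.** The strongest reply is that no error of arithmetic is shown: 10/24 agrees with 0.41 apart from truncation, the SAP never says that 10 Nm is a four-visit average, and the rest is a matter of unstated inputs. The first two parts stand. The SAP does not define the 10 Nm as an average, and 0.4167 is also the f for a single visit. But the single-visit reading does not rescue the figure: "an effect size of 0.41 and a significance level (alpha) of 0.05 using two-way repeated measures ANOVA" ties 0.41 to the repeated measures analysis, and with a pre-operative visit among the four it describes a 10 Nm post-operative difference in neither term.

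It also stands that the route to 66 is not unique. A one-sided two-sample t test at d = 0.82 gives 66 (95.06%), and so does group-by-time with λ = 3(N − 2)f² and a non-sphericity correction of 0.45 to 0.46 (95.2% and 95.5%). A reader might infer that the trial was powered on the group term at ρ near 0.75, and so really has 79% power. The documents do not support that, because both the term and the correlation are guesses.

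The pattern 0/10/10/10 is likewise one choice among several. Only the zero before surgery follows from the design. The one-year source of the mean and SD could equally suggest 12 months only.

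One could add that the ANOVA yields both terms, and that under 0/10/10/10 the better of the two never falls below 91.1% (lowest near ρ = 0.43). That comfort is limited. It picks the better of two tests, each at 0.05, with no prior choice between them. It also fails for 12 months only, where at ρ = 0.3 the terms have 23% and 84%, and at ρ = 0 they have 39% and 68%.

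**Conclusion.** The point holds: 0.41 is not the effect size for a 10 Nm post-operative difference in either between-group term of the planned ANOVA, and the 95% attached to 66 patients is unsupported. This goes beyond missing detail, because the trial's own visit schedule does not deliver the effect size it uses. For the group term the matching f is 0.3125 or 0.104, depending on the visits; for group-by-time it is 0.180 in both cases.

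A reader might go further and conclude that 66 is too few. The documents do not support this. Depending on the term, the correlation and the visits, power at 66 lies on either side of 95%. The powers given are illustrations that rest on equal allocation, a constant SD of 12, compound symmetry and no dropout. Confidence is high that the effect size does not match and that the inputs are missing; it is low for any single reconstruction of how 66 arose. The point should be fixed, but it does not call the trial's size into question.

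**What to change.** Keep 66 patients. In the sample-size paragraph, replace f = 0.41 with the value for the assumed difference at each visit (zero pre-operatively), name the ANOVA term that decides the comparison and the assumed correlation among visits, and restate the power even if it is below 95%. Possible wording: *With 66 patients (33 per group), SD 12 and an assumed correlation of [value] among visits, the [group / group-by-time] term has [X]% power for differences of 0 Nm pre-operatively and [values] Nm at 3, 6 and 12 months.*

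If one year is the target, as the source of the mean and SD suggests, add a 12-month comparison of the groups adjusted for pre-operative torque and state its power: about 91% unadjusted and two-sided, about 95% adjusted if the correlation between pre-operative and 12-month torque is 0.4, and about 97% if it is 0.5.

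The cost is SAP wording, a stated power that may be lower than 95%, and, if the 12-month option is taken, one comparison that the SAP does not now contain. No extra patients or measurements are needed, since pre-operative torque is already collected.

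### Torque is compared in absolute Nm with no covariate for sex or body mass, so a between-group comparison is less precise than the same 66 patients allow

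*Combined protocol and SAP*

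**What the plan says.** The SAP section takes its planning values from a prior study: a "mean knee extensor peak torque at one year postoperatively, 53.9 Nm, and the standard deviation, 12". The sample size is built on "power of 95% in detecting a 10 Nm difference in the extensor peak torque, with a standard deviation of 12", and the inputs are completed by "with a standard deviation of 12, 4 measurements, an effect size of 0.41" and "a significance level (alpha) of 0.05 using two-way repeated measures ANOVA". The target is in Nm and is not divided by body mass.

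The Design and Methods section says "Sixty-six patients diagnosed with primary knee osteoarthritis will be randomly assigned to either the UC or the PS group". It names no stratification factor. Measurements are taken before surgery and at 3, 6 and 12 months.

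On analysis, the SAP says only "Two-way repeated measures ANOVA will be used for the statistical analysis of the repeated measurements in the two groups". It names no covariate, and it does not say whether the group main effect, the group-by-time interaction or a particular visit decides the comparison. Sex and body mass are not mentioned anywhere in the document.

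**The concern.** Absolute torque can be expected to vary with a patient's sex and body size, and the choice of insert changes neither. An unadjusted comparison of group levels leaves that variation in the error term. If one arm happens to receive more large or male patients, nothing in the model corrects for it. At stake is the width of the interval around the UC–PS difference. The information that could narrow it would probably be on file before surgery and would need no extra patients or visits.

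**Working it through.** **Inputs from the SAP.** Difference 10 Nm, SD 12, effect size f = 0.41 (10/12/2 = 0.417), m = 4 measurements, alpha 0.05, N = 66.

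**Assumed, because not stated.** Equal allocation (33 per arm); the correlation rho between visits; and R², the share of single-visit torque variance explained by sex and body mass, taken as 0.1 to 0.4.

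**Step 1: which test does 66 belong to?** For the between-group main effect, the noncentrality is lambda = f²·N·m / (1 + (m−1)·rho), on 1 and N−2 degrees of freedom.
- With f = 0.41 and rho = 0.75: lambda = 0.1681 × 66 × 4 / 3.25 = 13.65 and power = 95.3%. The smallest even N reaching 95% is 66.
- With f = 0.417, rho = 0.8 also gives 66.
- The within-between interaction with f = 0.41 needs only 28 patients (rho 0) or 16 (rho 0.5).

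The figure therefore fits the main effect, with an unstated rho of about 0.75 to 0.8.

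**Step 2: 12-month comparison.** Residual SD = 12·√(1−R²); SE = SD·√(2/33); half-width = t(0.975)·SE. Power comes from the noncentral t, with 64 error df unadjusted and 62 with two covariates.

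| R² | SD | SE (Nm) | 95% CI half-width (Nm) | Power for 10 Nm |
|---|---|---|---|---|
| 0 | 12.00 | 2.95 | 5.90 | 91.5% |
| 0.1 | 11.38 | 2.80 | 5.60 | 94.0% |
| 0.2 | 10.73 | 2.64 | 5.28 | 96.1% |
| 0.3 | 10.04 | 2.47 | 4.94 | 97.8% |
| 0.4 | 9.30 | 2.29 | 4.57 | 99.0% |

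**Step 3: main effect over four visits.** At rho = 0.75 the variance of one patient's four-visit mean is 144 × (1 + 3 × 0.75)/4 = 117. If the explained part is wholly stable, adjustment subtracts 144·R².
- R² = 0.1: (117 − 14.4)/117 = 0.877, square root 0.936, so the SE falls by about 6%.
- R² = 0.4: (117 − 57.6)/117 = 0.508, square root 0.713, so the SE falls by about 29%.

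**Step 4: group-by-time or change.** The variance of the 12-month change is 2·144·(1−rho). At rho = 0.75 this is 72, so the SD is 8.49 Nm. A stable additive size effect lowers the variance and the covariance by the same amount, so the SD stays at 8.49 Nm at every R². There is no gain.

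**Step 5: gain beyond pre-operative torque.** Let r be the pre/post correlation, q the share of post-operative variance explained by sex and mass, and c the share of post-operative variance that is stable capacity. If size and pre-operative torque are related only through that capacity, their correlation is x = r·√q/c. The two-predictor fit is then R² = (r² + q − 2·r·√q·x)/(1 − x²), compared with r² for torque alone. With r = 0.7, torque alone leaves 1 − 0.49 = 0.51 of the variance.
- c = 0.85: residual 0.4685 (q = 0.2) or 0.4115 (q = 0.4), a further cut of 8% or 19%.
- c = 0.70: residual 0.4875 or 0.450, a further cut of 4% or 12%.

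The range is therefore about 4% to 19% of residual variance, or roughly 2% to 10% off the SE.

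**The case against.** The strongest reply is that the plan is valid as it stands. Randomisation protects against systematic imbalance, and chance imbalance is already part of the standard error and the 5% type I error. The SD of 12 is unadjusted, so it already contains whatever spread of body size the prior cohort had, and the sample size has budgeted for that noise. All of this stands, and it limits the point to precision.

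The second reply is that pre-operative torque is one of the four measurements, so a group-by-time reading of the same ANOVA already cancels stable size differences. This is correct (step 4). But the SAP does not commit to that reading, and its sample size points to the main effect. The unnamed deciding effect is the more basic gap.

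The third reply is that pre-operative torque as a covariate would do much of the work. That also stands: what sex and body mass add is modest, and it depends on assumptions that the documents cannot settle.

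A reader might go further and infer that a mixed-sex sample leaves the trial short of power, by treating 12 as the SD within one sex and adding a gap between men and women. The documents do not support this. They give 12 as the SD reported with the 53.9 Nm mean and say nothing about sex. With an overall SD of 12 and an assumed 20% men, a 30 Nm gap would contribute 0.2 × 0.8 × 900 = 144, which is the entire variance and leaves none within either sex.

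**Conclusion.** The point holds as a matter of lost precision. For the test that matches N = 66, or for a 12-month comparison, stable sex and body-mass differences stay in the error term, and pre-specified covariates would reduce, not remove, their contribution. Under an assumed R² of 0.1 to 0.4, the 12-month half-width narrows by 0.3 to 1.3 Nm and the main-effect SE falls by about 6% to 29% (at rho 0.75, with a wholly stable size effect). Neither R² nor rho is in the documents. The added value is smaller beside pre-operative torque, and absent for a group-by-time or change test with a stable additive size effect.

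It would be wrong to conclude that the planned comparison is biased, or that this omission leaves the trial underpowered. This is a cheap improvement to a valid analysis.

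**What to change.** Before unblinding, add to the SAP:
- the effect and time point that decide the comparison of extensor peak torque;
- sex (factor) and pre-operative body mass (kg, continuous), alongside pre-operative torque, as covariates in the model for the between-group comparison of torque. Pre-operative torque then serves as a covariate, and the 3-, 6- and 12-month values are the repeated outcomes;
- Nm as the unit, so that the 10 Nm target keeps its meaning.

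The cost is a few sentences and 2 further error degrees of freedom for sex and body mass (64 to 62 before pre-operative torque is counted). No patients, visits or tests are added. The fix assumes that sex and weight are recorded before surgery for every patient, which is reasonable but not stated, so the sponsor should confirm it.

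### Does the SAP need to promise a UC–PS difference with a 95% confidence interval for extensor peak torque?

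*Combined protocol and SAP*

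**What the plan says.** The Objective is to "compare the isokinetic performance and clinical outcomes of these inserts in PCL sacrificing TKA". Under Design and Methods, outcomes are "recorded preoperatively and at 3, 6 and 12 months postoperatively". The SAP takes its sizing inputs from a prior study's "mean knee extensor peak torque at one year postoperatively, 53.9 Nm" and SD of 12. It aims at "detecting a 10 Nm difference in the extensor peak torque". The remaining sizing inputs are listed as "with a standard deviation of 12, 4 measurements, an effect size of 0.41", and the calculation arrives at 66 patients for 95% power.

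Three sentences cover analysis and reporting. On presentation the SAP says "All the data will be presented as means and standard deviations". On the method of analysis it says "Two-way repeated measures ANOVA will be used for the statistical analysis of the repeated measurements in the two groups". On the decision rule it says "Values of $p < 0.05$ will be considered statistically significant". The plan names no between-group difference, confidence interval, contrast or time point for any outcome. It also makes no claim of equivalence and gives no rule for interpreting a non-significant result.

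**The concern.** The trial exists to compare two inserts, yet the stated outputs are per-group summaries and a significance verdict. Neither planned test gives a 12-month difference in Nm. The group effect averages four visits, one of them preoperative, and the group-by-time interaction has 3 degrees of freedom.

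With two established inserts, a non-significant result is quite possible. The reader then wants to know whether a difference as large as the sizing figure has been ruled out, and a p-value above 0.05 does not say. If the interval were both needed and unobtainable, a null result could be taken as showing that the inserts perform alike when the data still allowed 10 Nm.

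**Working it through.** **Inputs.** From the SAP: 10 Nm, SD 12, 4 measurements, effect size 0.41, alpha 0.05, 66 patients, 95% power. Assumed: 33 per arm (no allocation ratio is stated), SD 12 at every visit, equal correlation rho between visits (none is stated, so a range is shown), and a true difference of zero.

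**The plan's own figure.** The effect size is (10/12)/2 = 0.417, stated as 0.41. For the between-group test in a repeated measures ANOVA the noncentrality is f² × N × 4/(1 + 3 × rho), on 1 and N − 2 degrees of freedom. With f = 0.41 and N = 66 the numerator is 0.1681 × 66 × 4 = 44.38.

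- rho 0.5: 44.38/2.5 = 17.75, power 0.986 (52 patients would reach 95%).
- rho 0.75: 44.38/3.25 = 13.65, power 0.953 (66 patients needed).
- rho 0.8: 44.38/3.4 = 13.05, power 0.945 (68 needed).

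So 66 is consistent with the group effect at a correlation of about 0.75. That is an inference from the result, not something the SAP says.

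**Interval at a single visit.** SE = 12 × √(2/33) = 2.954 Nm. With 64 degrees of freedom, t = 1.998 and the half-width is 5.90 Nm.

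- Observed 4 Nm: CI −1.9 to 9.9, p = 0.18. This excludes 10 Nm.
- Observed 5 Nm: CI −0.9 to 10.9, p = 0.10. This does not.

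A result is non-significant with an interval reaching 10 Nm in either direction when the observed difference lies between 10 − 5.90 = 4.10 and 5.90 Nm in absolute size. With no true difference this happens in 12.0% of trials.

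**Interval for the planned group effect (average of four visits).** SE = 2.954 × √((1 + 3 × rho)/4).

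| rho | SE | Half-width | Ambiguous range (Nm) | Share of null trials | Same, SD estimated in each trial |
|---|---|---|---|---|---|
| 0.5 | 2.335 | 4.67 | none | 0% | 0.3% |
| 0.75 | 2.663 | 5.32 | 4.68 to 5.32 | 3.3% | 4.0% |
| 0.8 | 2.724 | 5.44 | 4.56 to 5.44 | 4.8% | 5.4% |

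The ambiguous range opens only when the half-width passes 5 Nm: (5/5.90)² = 0.718, and (4 × 0.718 − 1)/3 gives rho = 0.62. At rho 0.75, an observed 4 Nm gives CI −1.3 to 9.3 (p = 0.14) and 5 Nm gives −0.3 to 10.3 (p = 0.065).

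**Can the interval be recovered?** At a single visit, yes: means, SDs and group sizes give the SE above. For the group effect, SE = |difference|/√F. In one simulated data set (33 per arm, rho 0.75) this gave 2.527, equal to the SE computed directly. It needs F or an exact p, which the SAP neither promises nor rules out.

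**Would adding an interval change a conclusion?** It would not narrow the interval or reduce the 12%; the same trials would still reach 10 Nm. It could also introduce an inconsistency. If the interval were for 12 months while the p-value came from the four-visit group effect, the two would disagree about significance in some null trials: by simulation about 4% at rho 0.75 (roughly 2% in each direction) and about 6% at rho 0.5.

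**The case for a change.** The strongest case for a change is that comparison is the stated aim, so the comparative estimate should be promised rather than left for readers to derive. The SAP says how all data will be presented, and that statement covers group summaries only. The addition would cost a sentence or two and no data. Naming the contrast in advance would also stop a visit being chosen after the results are known, which no reader's reconstruction can do. And for the group effect, means and SDs alone do not suffice.

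Much of this is true. The estimate and interval are absent from the text, and reporting them is better practice. But the presentation sentence excludes nothing, and a one-paragraph SAP does not list every output. Reporting the group difference with its interval is an ordinary step for an analyst who has fitted this ANOVA. The point about choosing a visit concerns something else: the SAP names no primary outcome, time point or ANOVA effect. A promise of an interval would not settle that, because the interval cannot be specified until the effect is named.

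The SAP also presents 10 Nm only as the difference to be detected and never calls it clinically important. Judging null results against it would give it a weight the plan does not claim.

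**Conclusion.** The observation is accurate, but it describes a reporting detail that analysts can fill sensibly, and no change to the plan is called for. The test, the sample size and the error rates are the same with or without a promised interval. For the planned group effect, ambiguity about 10 Nm affects 0% to about 5% of null trials over correlations of 0.5 to 0.8. For a single visit it affects about 12%, where the interval of ±5.9 Nm can be computed from summaries the SAP already promises. Neither figure is a rate of wrong conclusions, since the SAP claims no equivalence and sets no rule for reading a null result.

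These sizes rest on 33 per arm, SD 12 at every visit, equal correlations between visits and a true difference of zero. A larger SD would widen the intervals: at a single visit the half-width is 8.9 Nm if the SD is 18. The reasoning would be unchanged, because the interval would still be recoverable and the test unaffected. An analyst who does report an interval should attach it to the same effect as the p-value.

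### The SAP names no deciding term for its repeated measures ANOVA and appears to treat pre-operative torque as one of four outcomes; using it as a covariate, with one test fixed in advance, is a cheap improvement

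*Combined protocol and SAP*

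**What the plan says.** The Objective is "to compare the isokinetic performance and clinical outcomes of these inserts in PCL sacrificing TKA". Under Design and Methods, "isokinetic performance results for each patient will be recorded preoperatively and at 3, 6 and 12 months postoperatively": one visit before surgery and three after it.

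The Statistical Analysis Plan (SAP) sizes the trial "using the mean knee extensor peak torque at one year postoperatively, 53.9 Nm", and states: "A total of 66 patients is estimated to be needed to achieve a power of 95% in detecting a 10 Nm difference", "with a standard deviation of 12, 4 measurements, an effect size of 0.41". The analysis itself is: "Two-way repeated measures ANOVA will be used for the statistical analysis of the repeated measurements in the two groups". Reporting and significance are covered by "All the data will be presented as means and standard deviations" and "Values of $p < 0.05$ will be considered statistically significant".

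Nothing names the deciding term, a primary time point, a covariate, the assumed correlation between visits, the G*Power effect-size option or a sphericity correction.

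**The concern.** A two-way repeated measures ANOVA gives two tests that could answer the trial's question: group, and group-by-time. They test different hypotheses and can lead to different conclusions from the same data, so the 5% threshold has a clear meaning only once one of them is named.

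The schedule yields four measurements only if the pre-operative one is counted. Torque before surgery cannot be affected by the insert, and randomisation makes its expected group difference zero. If it is an outcome and the group term decides, the treatment effect is averaged with a visit at which no effect can exist. As a covariate, the same measurement would remove noise and would not dilute the effect.

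At stake are power on the group reading, the lack of a pre-specified difference with a confidence interval on the group-by-time reading, and the error rate if the choice between them stays open.

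**Working it through.** **Inputs from the SAP:** N = 66, difference 10 Nm, SD 12, f = 0.41, 4 measurements, alpha 0.05, power 95%.

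**Assumptions, not in the documents:** 1:1 allocation, SD 12 at every visit, complete data, and compound symmetry with correlation rho, shown at 0.3 / 0.5 / 0.75. Powers come from the noncentral F distribution with noncentrality λ.

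**1. The plan's own figure.** 10/(2 × 12) = 0.4167, close to the stated f = 0.41. For the group term, λ = f² × N × 4/(1 + 3 rho) with 1 and N − 2 df. At rho 0.75, λ = 0.1681 × 264/3.25 = 13.65 and power is 95.3%. N = 66 is the smallest even total reaching 95% for rho 0.74–0.77 (0.78–0.80 if f = 0.4167). For group-by-time, λ = f² × N × 4/(1 − rho) with 3 and 3(N − 2) df gives N = 28 at rho 0 and fewer as rho rises. Another convention, λ = f² × (N − 2) × 3 × eps, gives 38 at eps = 1 but 66 at eps = 0.45. The group term is therefore the best fit, not the only one.

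**2. Group term, sustained effect (0, 10, 10, 10 Nm).** The mean difference is 30/4 = 7.5 Nm, so f falls to 7.5/24 = 0.3125. λ = 7.5² × 66/[144(1 + 3 rho)] = 25.78/(1 + 3 rho) = 13.57 / 10.31 / 7.93. Power drops below 95% once rho exceeds about 0.31. Restoring 95% would take N = 86 at rho 0.5 or N = 112 at rho 0.75.

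**3. Group-by-time, same effect.** The squared deviations from 7.5 sum to 7.5² + 3 × 2.5² = 75. λ = (66/4) × 75/[144(1 − rho)] = 8.594/(1 − rho) = 12.28 / 17.19 / 34.38, with 3 and 192 df.

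**4. Pre-operative visit removed from the outcomes, no covariate.** For the three-visit mean, λ = 34.375/(1 + 2 rho) = 21.48 / 17.19 / 13.75, with 1 and 64 df.

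**5. Pre-operative torque as covariate.** For the three-visit average, λ = 11.458/[(1 + 2 rho)/3 − rho²] = 25.85 / 27.50 / 42.31. For month 12 alone, λ = 11.458/(1 − rho²) = 12.59 / 15.28 / 26.19. Both have 1 and 63 df. The joint test of all three visit differences uses λ = (66/4) d′A⁻¹d, where d holds the three differences and A is their adjusted covariance, with 3 and 61 df.

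Power (%) at rho 0.3 / 0.5 / 0.75; patterns are Nm at months 3, 6, 12:

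| Test | Sustained (10, 10, 10) | Growing (3.3, 6.7, 10) | Fading (10, 6.7, 3.3) | Early only (10, 10, 0) | Late only (0, 0, 10) |
|---|---|---|---|---|---|
| Group, four visits | 95.2 / 88.5 / 79.2 | 67.7 / 55.9 / 45.6 | as growing | as growing | 22.7 / 18.4 / 15.2 |
| Group-by-time | 84.1 / 94.6 / 99.9 | 70.6 / 85.5 / 99.3 | as growing | 93.5 / 98.7 / >99.9 | 84.1 / 94.6 / 99.9 |
| Three-visit mean, unadjusted | 99.5 / 98.3 / 95.5 | 86.1 / 77.7 / 68.3 | as growing | as growing | – |
| Adjusted average | 99.9 / 99.9 / >99.9 | 91.6 / 93.1 / 99.0 | as growing | as growing | 38.6 / 40.6 / 57.0 |
| Adjusted month 12 | 93.7 / 97.1 / 99.9 | 93.7 / 97.1 / 99.9 | 21.4 / 25.0 / 39.0 | 5 / 5 / 5 | 93.7 / 97.1 / 99.9 |
| Adjusted joint, 3 df | 99.2 / 99.5 / >99.9 | 90.0 / 93.8 / 99.6 | as growing | 98.1 / 99.5 / >99.9 | 86.9 / 95.0 / 99.9 |

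**6. Error rate.** Each term alone keeps 5% under compound symmetry. If either may be read as the result, the rate is 1 − 0.95² = 9.75% (simulated 9.7–10.0%).

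**7. Without compound symmetry** (pre-to-post correlation 0.3, post-to-post 0.75; simulated). Uncorrected group-by-time has a 6.9% error rate, and 4.7% with Greenhouse-Geisser. For a sustained effect, power is 87.6% for group, 83.8% for corrected group-by-time and 96.9% for the adjusted average. For a growing effect, the average has 72.5% against 77.6% for corrected group-by-time.

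**The case against.** The strongest reply is that the harm depends on readings the SAP never states. If group-by-time decides, nothing is diluted, and at the correlation implied by the sample size its power for a sustained effect is 99.9%. That stands: on this reading the power case for change is nil for a sustained effect near rho 0.75. What remains is a 3-df test with no single estimate, 84.1% power at rho 0.3, and a need for a sphericity correction.

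A reader might infer that the trial has only 79% power, or that 66 is wrong. The documents support neither. The 79.2% requires the group term and rho 0.75, both inferred, and the missing correlation leaves 66 neither confirmed nor refuted. A reader might also infer a false-positive rate near 10%. No sentence allows either term to count; the SAP merely does not exclude it.

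Nor is the covariate the main source of gain throughout. For a sustained effect, removing the pre-operative visit from the outcomes already lifts the group term to 99.5 / 98.3 / 95.5%, and the covariate adds at most about 4.5 points. It adds more for growing or fading effects: 86.1 / 77.7 / 68.3% becomes 91.6 / 93.1 / 99.0% for the average.

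Finally, either ANOVA term, named in advance and corrected where needed, is a valid test. The model proposed here is a better use of data already collected, not a repair of an invalid method.

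**Conclusion.** The point holds as a cheap improvement. That no deciding term is named is plain from the text. That pre-operative torque is an outcome is an inference, though no other count of the scheduled visits gives four. The group term as the basis of the sample size is a softer inference.

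Conditional on the group term, a sustained 10 Nm effect is estimated as 7.5 Nm, with power between 95.2% and 79.2% as rho goes from 0.3 to 0.75. Conditional on group-by-time, the shortfall is mainly in interpretation, plus power at low correlation. The 9.75% applies only if the choice of term is left until the results are known.

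The sizes rest on the stated assumptions, above all a correlation that the documents do not give. The absence of a named term does not depend on it.

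**What to change.** Replace the analysis sentence with wording such as:

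> Knee extensor peak torque at 3, 6 and 12 months will be analysed in a linear mixed model with unstructured covariance and fixed effects for group, visit, group-by-visit, pre-operative torque and pre-operative torque-by-visit, with Satterthwaite degrees of freedom. The deciding test, two-sided at 5%, is the adjusted UC–PS difference averaged equally over the three visits. Adjusted differences with 95% confidence intervals will be reported at each visit.

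The average is a workable default, not the only choice. The sponsor should fix one test before outcomes are seen by group, knowing the trade-offs:

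- **Average:** weak for late-only effects (39–57%, against 84–99.9% for group-by-time).
- **Month 12:** matches the one-year planning value, but is weak for fading effects (21–39%) and blind to early-only ones (5%). For a sustained effect at rho 0.3 it falls below the four-visit group term (93.7 against 95.2%).
- **Joint test:** define it as the UC–PS difference being zero at all three visits (group and group-by-visit together, 3 df). It has about 87% or more in every pattern tabulated, but gives no single estimate. The degrees-of-freedom method matters here: referring the unscaled statistic to 3 and 63 df would give about 5.6% error.

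Analyse the other repeated outcomes in the same way.

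If the four-measurement ANOVA is kept, name the deciding term, state the assumed correlation and the G*Power option, restate power for that term, and name a sphericity correction if it is group-by-time.

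The cost is SAP wording: no new patients, visits or data, and SPSS fits the model. The change does commit the sponsor to an estimand that the plan now leaves open.
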